- Mortality at D90
- Neurological functional status at D90
- Assessment of the patient's quality of life at D90
- Assessment of patient autonomy at D90
- Neurocognitive assessment of the patient at D90
- Estimation of the number of patients with post-traumatic stress symptoms at D90
- Length of stay in intensive care
- Duration of mechanical ventilation
- Need for vasopressor treatment in the first 72 hours

IV. Research design

A. Precise statement of primary and, where appropriate, secondary evaluation criteria

1. Primary endpoint

- Changes in serum levels of IL6 (inflammation marker) over the 48 hours following achievement of the thermal target (33°C) according to 2 reheating modalities during a targeted thermal control between 32.5° and 33.5°C: group with a slow reheating rate (RL; 0.25°C/h) compared with a group with a high reheating rate (RR; 0.5°C/h).
 - The choice of IL6 is based on the fact that it is one of the main interleukins produced during the inflammatory process. Several studies have demonstrated a strong correlation between IL6 levels and the neurological outcome of patients suffering cardiac arrest (57, 58). In addition, a description of the variations in IL6 during the performance of a 32.5-33.5 CCT after cardiac arrest has been carried out, making it possible to formulate the hypotheses necessary for calculating the number of patients in a cardiac arrest. (59).
 - H0 will be defined as the time at which the thermal target is reached, i.e. a body temperature of 33°C. This definition will make it possible to compare variations in inflammatory cytokines linked to rewarming rates and not to variations linked to the different times at which RTAs occur.
 - Given the high number of infectious complications expected (i.e. inhalation pneumonitis (49, 60)), given that it is not possible to perform a stratification on this pathology which nevertheless modifies the rates of IL6 (57) A record of these complications will be included in the data collection medium in order to ensure the homogeneity of the 2 groups of patients for these pathologies. Nevertheless, the diagnostic hypotheses take account of this high rate of infectious complications, since in the study used to formulate these hypotheses, patients who presented an infectious complication were included. (59). As for late complications, they may be linked to the rate of rewarming drawn at random by analogy with the infectious risk of hypothermia (61).

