- Estimation of the number of patients with post-traumatic stress symptoms assessed by the "Impact Event Scale Revised" questionnaire (75, 76) at D90. The Impact Event Scale-Revised (Appendix I) consists of 22 questions that assess stress reactions after a traumatic event, targeting psychological responses to intrusion and avoidance phenomena.
- Length of stay in intensive care.
- Duration of mechanical ventilation.
- Need for vasopressor treatment: comparison of doses of vasopressors in relation to weights (noradrenaline or adrenaline) required during the first 72 hours.

B. Description of the research methodology, accompanied by a schematic presentation specifying in particular the visits and examinations planned

1. Experimental design

This is a single-centre, open-label, randomised controlled clinical trial comparing two groups of patients successfully resuscitated for shockable rhythm RTA and presenting with persistent coma (Glasgow score less than or equal to 8) at inclusion: in the 2 groups, targeted temperature control between 32.5 and 33.5°C will be induced and maintained for 24 hours, then in the control group the rate of rewarming will be set at 0.5°C/h and in the intervention group it will be set at 0.25°C/h. In the 2 groups, a targeted control of the temperature between 36.5 and 37.5°C will be carried out for a total duration of 72 hours.

2. Conduct of the study

Inclusion period: 4 years and 6 months

Duration of a patient's participation in the study: 3 months maximum

Duration of statistical analysis: 3 months

Total duration of the study: 5 years

Each patient will benefit from a maximum follow-up of 3 months between the date of inclusion and the neurological assessment carried out at 3 months.

a) Inclusion

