The trial will be open-label, since the rewarming technique is performed by the medical team and the procedure is specific to the RR or RL group. However, this lack of blinding should not lead to bias since the primary endpoint is a biological assay and this is an objective criterion. (91). In addition, the assay will be performed blind to the randomisation group and centrally at the Nantes University Hospital. In addition, the **assessment of functional status neurological will be carried out at D90 by telephone in a blinded fashion by an independent psychologist who does not know the patient's randomisation group and is not participating in the study.**

c. Expected duration of participation of individuals and description of the chronology and duration of all trial periods, including follow-up, if applicable

The duration of patient follow-up in the study will depend on the patient's progress and will be a maximum of 90 days. Patients will be followed until they are discharged from hospital. Their living or deceased status will be determined on discharge from intensive care, from hospital and at D90. Their neurological status will be assessed at D90. It has been established that neurological functional assessment at D90 allows an assessment of neurological, functional and cognitive sequelae which are fixed without modification afterwards (92, 93). Assessments of quality of life, the existence of post-traumatic stress symptoms and the patient's autonomy will be carried out using specific questionnaires completed during a telephone interview with the patient by the independent psychologist responsible for the neurological assessment at D90. A neurocognitive assessment will also be carried out at D90 using the validated telephone version of the Mini Mental State Examination questionnaire.

1. Stopping a person's participation in research

Participation in the study will be discontinued in the event of secondary opposition from the patient or relatives.

2. Stopping part or all of the research

No interim analysis is planned as part of this research. However, in the case of this routine care study, if a consensus following a scientific publication were to call into question the main hypothesis or the management of patients treated by targeted temperature control between 32.5 and 33.5°C, this research could be stopped early at the decision of the sponsor.

II. Selecting and excluding people from research

A. Inclusion criteria for research subjects

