The primary endpoint will be analysed using a linear mixed model. If necessary, the data will be transformed beforehand.

Analysis of secondary endpoints

Secondary endpoints associated with a binary variable will be analysed using Fisher's exact test.

Secondary endpoints associated with a quantitative variable will be analysed using the same strategy as for the primary endpoint, using Student (or Wilcoxon) tests if the data are not repeated.

Finally, the parameters of the repeated measurements will be analysed using mixed models.

B. *Expected number of people to be included in the research, and expected number of people in each research location with statistical justification*

The headcount calculation is based on the work of Borm (99) and Vickers (100).

In this trial, the primary endpoint (interleukin 6 levels) is measured repeatedly. To calculate the number of patients required, the following parameters are required:

- The standard deviation of the interleukin 6 assay was set at 40 pg/ml.
- The main hypothesis is that a high heating rate ($>0.5^{\circ}\text{C}/\text{h}$) leads to an increase in inflammatory phenomena measured by IL6. In this case, according to previous studies (101) the mean level of IL6 expected in the slow rewarming group will be 100 pg/ml.
- A 15% increase (superiority analysis) in these phenomena is assumed (i.e. an IL6 level of 115 pg/ml in the RR group compared with 100 pg/ml in the RL group).
- The correlation between 2 measurements of interleukin 6 in the same subject was set at 0.85. This correlation was estimated by the manufacturer at 0.89, but we have chosen to adopt a slightly lower value, as a conservative approach.
- The errors of the first and second kind were set at 5% and 10% respectively.

If the trial were planned with a single interleukin 6 assay, it would be necessary to include 151 patients per group.

Taking into account a measurement of interleukin 6 at inclusion, and considering that the correlation between the assessments at inclusion and at H32 was 0.85, the number of patients was reduced to 42 per group.

Taking into account the fact that there were 2 intermediate assessments (H12, H24), and that the correlation between the assessments was 0.85, the number of patients was reduced to 25 per arm.

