Taking into account an estimated 20% of patients who may have been included but not randomised (patients who died or progressed to refractory shock despite treatment), the plan is to include 30 patients per group, i.e. a total of 60 patients.

C. *Expected level of statistical significance*

All statistical tests will be carried out with a significance level of 5%.

D. *Method for taking into account missing, unused or invalid data*

A second serum sample from each analysis will be kept locally after the first sample is sent to the laboratory (Nantes University Hospital) carrying out the centralised analyses, so that a "safety" sample can be sent in case the first sample is accidentally lost or destroyed.

Randomisation immediately before the start of the warm-up procedure will avoid missing data for the primary endpoint (Interleukin 6 assay).

E. *Managing changes to the initial strategy analysis plan*

The statistical analysis plan will be finalised when the database is frozen.

F. *Choosing the people to be included in the analyses*

The analysis will be carried out on an intention-to-treat basis.

VI. Justification for requesting validation of research in routine care

In accordance with the decree of 9 March 2007 and taking into account all the elements presented in the project, the person responsible for the research qualifies it as **research in routine care**, since :

- ✓ All procedures and protocols for targeted temperature control between 32.5 and 33.5°C are carried out as usual.
- ✓ The aim is to evaluate combinations of procedures and medical strategies for prevention and diagnosis (protocol for targeted temperature control between 32.5 and 33.5°C, determination of rewarming rate) that are standard practice, i.e. that are the subject of a professional consensus in compliance with their indications.
- ✓ This research does not focus on techniques or strategies that are either innovative or obsolete.
- ✓ The research compares two medical strategies (determining a fast or slow rate of rewarming during a period of targeted temperature control between 32.5 and 33.5°C), neither of which can, in the current state of knowledge, be considered superior to the other in terms of safety and efficacy. In fact, the North American recommendations do not specify a target heating rate. They only advise avoiding

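### Post-traumatic stress at D90 is measured with the 22-item IES-R but compared only as a count of patients with symptoms, so the score is not used and power is lost on one minor secondary endpoint

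*Combined protocol and SAP*

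**What the plan says.** III.B lists, among the outcomes on which the two groups are to be compared, "Estimation of the number of patients with post-traumatic stress symptoms at D90". IV.A.2 repeats this as the criterion ("Estimation of the number of patients with post-traumatic stress symptoms assessed by the" IES-R) and says that the instrument "consists of 22 questions that assess stress reactions after a traumatic event". The section on expected duration of participation has the independent psychologist collect the D90 questionnaires by telephone and describes this item as "the existence of post-traumatic stress symptoms". All three places treat it as present or absent in each patient.

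V.A names no individual scale. It sets two general rules: "Secondary endpoints associated with a binary variable will be analysed using Fisher's exact test", and "Secondary endpoints associated with a quantitative variable will be analysed using the same strategy" as the primary endpoint, "using Student (or Wilcoxon) tests if the data are not repeated". Fisher's test for the IES-R endpoint is therefore an inference from the general rule, though a direct one.

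The supplied text contains no planned comparison of the IES-R score and no threshold for having symptoms. Appendix I, which holds the questionnaire, is not among the supplied pages.

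**The concern.** A graded instrument is collected and then reduced to yes or no before the arms are compared. Patients just above and far above the threshold become identical, and patients just either side of it become opposites. The plan already has a suitable test for an unrepeated quantitative outcome, but the way this endpoint is worded steers it away from that test.

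The sample is small. About 25 patients per arm are to be randomised, and only survivors able to answer a telephone questionnaire contribute. With so few, the binary result can turn on one person. At 13 per arm, 1 versus 7 patients with symptoms gives Fisher p = 0.030, while 1 versus 6 gives p = 0.073.

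**Working it through.** **What the plan gives.** It states no power, effect, SD or prevalence for this endpoint, so there is no planned figure to reproduce. Two inputs carry over from elsewhere.

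- Randomised patients: 25 per arm (V.B).
- Level: 5% (V.C), sidedness not stated. I used two-sided, because that is what reproduces the single-assay figure of 151 per group in V.B: 2 × (1.960 + 1.282)² × (40/15)² = 149.4, so 150, and 150.4 with the t correction, which rounds up to 151. A one-sided test would need 122.

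**Number interviewed (assumption).** II.A.3 quotes good-outcome rates of 49% and 55% in the cooled arms of two earlier trials. Applied here: 0.49 × 25 = 12.3 and 0.55 × 25 = 13.8, so about 12 to 14 per arm. I used 10, 13 and 16 to bracket this. Ten is pessimistic: it corresponds to the 39% rate of a normothermia arm (0.39 × 25 = 9.8), whereas everyone in this trial is cooled.

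**Score and cut (assumptions).** Normal score; shift d = 0.8 SD; proportion p1 with symptoms in the better arm of 15, 25 or 40%. The other arm follows from the same shift, with z the standard normal point exceeded with probability p1: p2 = 1 − Φ(z − d).

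- p1 = 0.15: 1.036 − 0.8 = 0.236, so p2 = 0.407
- p1 = 0.25: 0.674 − 0.8 = −0.126, so p2 = 0.550
- p1 = 0.40: 0.253 − 0.8 = −0.547, so p2 = 0.708

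**Power.** For Fisher, the exact sum of Bin(a; n, p1) × Bin(b; n, p2) over all tables with two-sided p ≤ 0.05. For Wilcoxon, 20,000 simulated trials per setting. To separate the cut from Fisher's conservatism, the count was also tested with Boschloo's exact test, which is less conservative.

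| Per arm | Wilcoxon, score | Fisher, count | Boschloo, count |
|---|---|---|---|
| 10 | 36% | 10–13% | 21–26% |
| 13 | 46% | 19–27% | 31–32% |
| 16 | 56% | 23–29% | 30–39% |

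**Loss, score to Fisher.** Smallest, at 13 per arm and p1 = 0.40: 45.7 − 27.2 = 18.5 points. Largest, at 16 per arm and p1 = 0.15: 55.4 − 22.8 = 32.6 points. Hence about 18 to 33.

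**Loss from the cut alone, score to Boschloo.** About 10 points (36 − 26, at 10 per arm) to roughly 20. The upper end depends on how the two-sided Boschloo test is built. With the doubled one-sided version it is about 21. With tables ordered by the two-sided Fisher p-value, one setting (16 per arm, p1 = 0.15) reaches 56 − 30 = 26.

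**Smaller effects.** The only effect in the plan is for IL6: 15/40 = 0.375 SD. Over 0.375 to 0.5 SD and 10 to 16 per arm, the score has 11 to 26% power and Fisher 2 to 12%.

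**The case against.** The plan consistently defines the target as how many patients have symptoms, a quantity that clinicians read easily. It is one of many secondary endpoints for which the trial was not sized. The 0.8 SD effect is a reviewer's assumption, about twice the only standardised effect in the plan, and at that smaller effect neither analysis would be likely to change a conclusion. The analysis plan is to be finalised at database freeze, and Appendix I may contain a scoring rule. All of this stands, and it limits the weight of the point. It does not turn the count into the better comparison, since III.B says that the groups are to be compared on it and the score is available from the same questionnaire.

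Four stronger readings are tempting and are not supported.

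- A reader might put the whole 18 to 33 points down to the cut. A substantial part is Fisher's conservatism.
- A reader might say that the cut removes most of the available power. At 13 and 16 per arm, with Boschloo's test, it removes less than half.
- A reader might conclude that no threshold exists. The appendix is not supplied, so its absence from the plan cannot be claimed.
- A reader might think that the IES-R is singled out. CPC is also dichotomised, although IV.A.2 defines that split (1–2 versus 3–5).

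A larger loss, 22 to 45 points, appears if Student's test is the comparator, 12 to 25 patients per arm are interviewed and prevalence is 10 to 50%. Its upper end needs nearly every randomised patient to be interviewed, which the background survival figures make unlikely.

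**Conclusion.** The point holds as a minor one. As worded, the plan compares the arms on a yes/no reduction of the IES-R and never on its score. Under the stated assumptions this leaves power of 10 to 29% where the score would give about 36 to 56%. The direction does not depend on the assumptions; the size does, because the number interviewed, the prevalence, the effect and the shape of the score are all assumed. Even the score is underpowered here, so the gain is a better estimate with an interpretable interval rather than a decisive test. The primary endpoint and the sample size are unaffected.

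**What to change.** In IV.A.2 and V.A, name the IES-R total score at D90 as the compared variable, tested under the existing Student/Wilcoxon rule, and report the difference with its 95% CI. Report the number of patients above the cut descriptively, as n/N of interviewed survivors in each arm, without a separate test. Align the wording in III.B. Settling this before the database freeze also prevents a later choice between score and count.

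The cost is wording only: no new data, visits, staff or patients, and no additional test. The one drawback is that a score difference is less immediate to clinicians than a count, which is why the count is kept as a description.

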- Slow, gradual and controlled rewarming allows better control of vasoplegia secondary to rewarming. (44) and thus reduces the risk of cardiovascular collapse during this phase, which can have an impact on neurological prognosis.
- In the different context of haemorrhagic shock and in animal experiments, it has been shown that a rapid rewarming rate leads to increased mortality, with surviving animals also showing neurological dysfunctions (45).
- Rapid warming can lead to increased CO₂ production associated with disorders of cerebral vasoreactivity (46) resulting in a sudden increase in intracranial pressure (26, 47).
- Once rewarming has been achieved, it is preferable to avoid the onset of "rebound" hyperthermia, even if no clinical study has yet formally demonstrated the impact of this measure. (48). It is not known whether this is a direct deleterious effect of hyperthermia or a risk associated with CCT 32-34 through hyperthermic rebound after rewarming with activation of inflammatory cytokines, or whether it is a consequence of the infectious complications that are frequent in this context. (49). Nevertheless, slow rewarming allows better control of this phase (50).
- Rapid reheating can expose the cerebral circulation to temperatures above 37°C due to thermopooling phenomena, resulting in harmful localised hyperthermia (51).
- A Dutch team (52) observed that a rapid rewarming rate (>0.5°C/h) was associated with an unfavourable neurological prognosis at 6 months compared with a slow rewarming rate (<0.5°C/h), although this difference was no longer significant after adjustment for confounding factors.

b) Arguments in favour of rapid warming :

- An American study (53) observed that cerebral vasoreactivity was preserved when CCT 32-34 was performed after RTA. In addition, this study showed that during the hypothermia period, there was an increase in cerebral vascular resistance, which could lead to a reduction in cerebral perfusion. In view of these factors, rapid rewarming should enable cerebral perfusion to be rapidly normalised while preserving cerebral vasoreactivity.
- In the context of passive rewarming after CCT 32-34 for RTA, a Swiss team observed that a prolonged duration (600 minutes Vs 479 minutes) of rewarming was associated with an increase in mortality (54). However, it is possible that this difference in prognosis linked to the duration of rewarming, as in the

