Randomisation will be carried out within a 6-hour time window, the end of which will be determined by the 24^{ème} hour after the target temperature of 33° is reached (i.e. H24). This time window will therefore be between H18 and H24. This method will make it possible not to randomise patients

who have had an unfavourable outcome between inclusion and the start of the rewarming period (death following a refractory state of shock). This randomisation will be carried out via computerised data collection (eCRF): the patient will then be assigned to a randomisation arm: RL group or RR group.

b) Performing sedation/analgesia

This sedation/analgesia will be carried out in the 2 groups (RR and RL) during the period of hypothermia and rewarming until a temperature of 36°C is reached:

- Continuous administration of a hypnotic (midazolam, propofol) at a titrated dose to obtain a RASS score of -5 in both groups.
- Continuous administration of a morphine (fentanyl, sufentanil, remifentanil) at a titrated dose to obtain a RASS score of -5 and the absence of painful symptoms using the usual scales (behavioural pain scale) in the 2 groups.

This sedation/analgesia will be discontinued once a temperature of 36° Celsius has been reached.

In the event of haemodynamic, respiratory or neurological instability (agitation, risk of self-extubation in particular), this sedation/analgesia may be continued beyond this period. This continuation will be recorded in the eCRF.

c) Shiver management strategy

In accordance with the published protocol for the intensive care unit at La Roche Sur Yon (78) the treatment strategy for shivering will initially be based on boluses of hypnotics and morphine, followed by curare as a last resort (50, 79). The severity of shivering should be assessed using the Bedside Shivering Assessment Scale (see appendix C), which has been validated and is correlated with the increase in metabolic demand associated with shivering phenomena (80). The aim is to obtain a BSAS score ≤ 1 .

- Level 1 treatment for chills :
 - A bolus corresponding to a dose equal to the flow rate of the electric syringe administering the continuous infusion of the hypnotic and morphine administered (e.g. for an electric syringe flow rate of 5mg/h, a bolus of 5mg of the product concerned will be injected).
- Level 2 treatment for chills :
 - After failure of level 1

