 - Bolus of non-depolarising curares: cisatracurium besilate (Nimbex®) bolus 0.1mg/kg, atracurium besilate (Tracrium®) bolus 0.5mg/kg
- Level 3 treatment for chills :
 - After failure of level 2
 - Bolus and maintenance of non-depolarising curares with monitoring of the BSAS score for a target ≤ 1 : cisatracurium besilate (Nimbex®) boli 0.1mg/kg then 10mg/h with increase and decrease in steps of 1mg/h with a target BSAS score ≤ 1 . If a curare infusion is started, it can be stopped once the warming phase has begun and a temperature of 35°C has been reached.

d) Management strategy for targeted temperature control between 32.5 and 33.5°C

Targeted temperature control between 32.5 and 33.5°C will be achieved using an external thermal regulation device of the ArticSun type (BARD, Louisville, Colorado, USA). The protocol will enable a number of parameters to be standardised: sedation, possible curarisation, management of expected adverse effects.

Indeed, although there are numerous methods available to date, none of which has demonstrated its superiority in achieving targeted temperature control between 32.5 and 33.5°C in the management of RTA (active external cooling (15, 16, 81-83)active internal cooling (84, 85)internal cooling with infusion of ice-cold isotonic saline solution (81, 86)), the active external device allows continuous control of temperature and the desired rate of rewarming, which is the subject of this study. In addition, the intensive care unit at La Roche Sur Yon already uses this type of device to perform the 32.5-33.5° CCT, and has the technical expertise to use it routinely.

The implementation protocol for CCT 32.5-33.5 breaks down as follows:

- Rapid intravenous injection of 1500 ml of isotonic saline at 4°C. This technique enables the target temperature to be reached rapidly, with a high safety profile (81, 87).
- After fitting the specific pads, induction continued and hypothermia was maintained at a target temperature of 33°C (allowing the same target temperature to be chosen for the 2 randomisation groups) for 24 hours.
- H0 is defined as the time at which the patient's body temperature reaches 33°C. Taking the sample.
- H12: sample taken
- Time window H18-H24: randomisation via the eCRF.
- H24: sampling and modification of the target internal temperature according to the software for a target of 37°C with a heating rate set according to the randomisation group (0.5°C/h for RR or 0.25°C/h for RL).

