b) Patient follow-up

Analyses will be carried out locally or off-site depending on the examinations concerned:

Off-site analyses (CHU Nantes): II2, II4, II6, II8, II10, GM-CSF, TNF-alpha, INF-beta, neurofilament. All these analyses can be performed using a 5 ml blood tube for all the analyses (i.e. a total of 60 ml of blood taken, taking into account the safety sample kept on the investigator's site). The principles of the LuminexTM assay and the Patrol test are explained in appendix J.

Local tests: blood count, arterial blood gases (pH, pO₂, pCO₂, HCO₃), lactates, blood ionogram (Na, K, Cl, Urea, Creatinemia, Ca), troponin, CRP, procalcitonin.

Local examination: 12-lead electrocardiogram

Neurological analysis using the CPC score will be carried out by telephone by an expert blinded to the randomisation group (psychologist carrying out a semi-directive interview, blinded to the randomisation group).

Flow Chart :

	Inclusion	J0	J1	J2	Jn	J90
Eligibility: check the study's eligibility criteria	X					
Informing the next of kin with a cooling-off period	X					
No-objection search	X					
Demographic data	X					
Randomisation		X				
Patient characteristics	X					
Data : coronary angiography	X					
Data: ventilation	X	X	X	X	X	
Biology	X	X	X	X		
Electrocardiogram	X		X	X		
Clinical evaluation	X		X	X	X	X
Treatments administered		X	X	X	X	
Definitive extubation					X	X
Living / Deceased		X	X	X	X	X
Blind neurological assessment by a psychologist						X

D0 corresponds to the start of the hypothermia procedure.

Jn corresponds to discharge from intensive care

B. Description of measures taken to reduce and avoid bias

1. Prize draw

This randomisation will be carried out directly on the electronic observation notebook provided (see Data collection). Randomisation will be carried out according to a 1:1 ratio with blocks of variable size, as the study will be open-label. No stratification factors will be taken into account. Randomisation will be generated by the CIC INSERM 1415 biometrics unit, which is independent of the patient recruitment process. It will be carried out within a time window of 6 hours, the end of which will correspond to the end of the CCT 32.5-33.5 period (i.e. between H18 and H24). This delayed randomisation will allow only patients alive at the end of the 32.5-33.5 CCT period to be randomised, and not patients who died during the first phase (e.g. progressing to refractory shock).

2. Blinding method

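### The vasopressor endpoint's 72-hour window has no stated start; from either time origin the protocol defines, it includes pre-randomisation treatment and dilutes any rewarming effect

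*Combined protocol and SAP*

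**What the plan says.** The secondary objectives (III.B) list "Need for vasopressor treatment in the first 72 hours". The secondary criteria (IV.A.2) make this a dose measure: "comparison of doses of vasopressors in relation to weights (noradrenaline or adrenaline) required during the first 72 hours". Neither place gives a start for the 72 hours.

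The timeline is fixed elsewhere:

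- The temperature management section (IV.B.2.d) states: "H0 is defined as the time at which the patient's body temperature reaches 33°C".
- The note under the flow chart states: "D0 corresponds to the start of the hypothermia procedure". Cooling begins before 33°C is reached, so D0 comes before H0.
- On randomisation, the Inclusion section (IV.B.2.a) states: "This time window will therefore be between H18 and H24".
- The arms separate at "H24: sampling and modification of the target internal temperature according to the software for a target of 37°C", with the rate set by arm: "0.5°C/h for RR or 0.25°C/h for RL".

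The Statistics section (A, planned methods) assigns Fisher's exact test to binary secondary endpoints, Student or Wilcoxon tests to quantitative endpoints measured once, and mixed models to repeated measurements. It names no baseline covariate for vasopressor dose. Randomisation is unstratified.

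**The concern.** Until H24 both arms receive the same temperature protocol, so vasopressor given before then cannot reflect the rewarming rate. Early use is likely: the non-inclusion criteria exclude only patients needing more than 1 µg/kg/min of noradrenaline or adrenaline.

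The protocol's haemodynamic argument is specific to rewarming. Slow rewarming is said to limit vasoplegia and "thus reduces the risk of cardiovascular collapse during this phase" (II.A.5.a). The design also delays randomisation so that patients lost early to refractory shock are not allocated. A window starting at D0 or H0 brings that early period back into the outcome. At stake is the trial's ability to see a haemodynamic effect of rewarming rate if there is one.

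**Working it through.** **No figure to reproduce.** The plan gives no effect size, SD or power for this endpoint. The 25 patients per arm used in step 4 come from its IL6 calculation.

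**Step 1. Share of the window before the arms differ.**

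| Clock starts at | Before randomisation | Before rewarming |
|---|---|---|
| H0 | 18/72 to 24/72 = 25 to 33% | 24/72 = 33% |
| D0, assuming 2 to 8 h to reach 33°C | 20/72 to 32/72 = 28 to 44% | 26/72 to 32/72 = 36 to 44% |
| Randomisation or H24 | 0% | 6 h at most, or 0% |

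The time needed to reach 33°C is an assumption, because the documents do not give it. They do not state the last row as the start.

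**Step 2. Dilution of the difference.** From H0, the 72-hour mean is (1/3) × early mean + (2/3) × late mean. The expected early difference is zero. A late difference d therefore becomes (2/3)d = 0.67d.

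**Step 3. Cost in patients.** Let k be the ratio of early to late SD and c the correlation between early and late dose; both are assumed. With late SD 1, the variance of the 72-hour mean is k²/9 + 4/9 + 4ck/9. Dividing by the squared dilution factor (4/9) gives the sample-size ratio against H24 to H72 alone:

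ratio = 1 + k²/4 + ck

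| k | c | Ratio |
|---|---|---|
| 0.5 | 0.3 | 1 + 0.0625 + 0.15 = 1.21 |
| 1 | 0.3 | 1 + 0.25 + 0.30 = 1.55 |
| 1 | 0.5 | 1 + 0.25 + 0.50 = 1.75 |
| 1 | 0.7 | 1 + 0.25 + 0.70 = 1.95 |
| 2 | 0.3 | 1 + 1 + 0.60 = 2.60 |
| 2 | 0.85 | 1 + 1 + 1.70 = 3.70 |

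Adjusting the H24 to H72 dose for the pre-rewarming dose multiplies its variance by 1 − c². At k = 1 and c = 0.5, the 72-hour mean then needs 1.75/0.75 = 2.33 times the patients of the adjusted analysis.

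**Step 4. Illustration with 25 per arm.** Assume a true late effect of 0.8 SD, two-sided 5%, normal approximation. Power = Φ(effect × √(25/2) − 1.96), with k = 1 and c = 0.5:

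- H24 to H72 alone: 0.8 × 3.536 − 1.96 = 0.87, power 81%.
- 72-hour mean from H0: the effect is 0.8/√1.75 = 0.605, so 0.605 × 3.536 − 1.96 = 0.18, power 57%. Over k 0.5 to 2 and c 0.3 to 0.85 the range is 31% to 73%.
- H24 to H72 adjusted for earlier dose: the effect is 0.8/√0.75 = 0.924, so 0.924 × 3.536 − 1.96 = 1.31, power 90%.

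Steps 3 and 4 treat dose as a mean with equal variance in the two arms. Real doses are likely to be skewed with many zeros, so the figures indicate order of size only.

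**The case against.** The strongest reply is that the text leaves the start open and therefore does not commit the trial to a poor window. That is correct, and a fixed share of one third cannot be read out of the plan: it is exact only for rewarming counted from H0. But both origins the protocol defines lie before allocation, and nothing points to a later start. Section IV.B.1 mentions another 72 hours, for control at 36.5 to 37.5°C, without linking it to this endpoint. The study diagrams were not visible in the text reviewed and should be checked for a marked window.

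A second reply is that repeated doses may go to a mixed model. One that treated doses before H24 as baseline would avoid the dilution. The plan does not specify that for vasopressors.

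A third is that the proposed window is itself diluted. From 33 to 37°C takes 4/0.5 = 8 h or 4/0.25 = 16 h, so rewarming differs only until H40, leaving 32 of the 48 hours after it. This is fair as to the size of effect, but dose after H40 can still be a consequence of the allocated rate. Dose before H24 cannot.

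Some stronger readings are tempting but unsupported:

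- **Bias between arms.** Pre-allocation doses are equal in expectation, so the mechanism is dilution and added noise.
- **An outcome dominated by early shock.** The documents contain no vasopressor dose data, and from H0 two thirds of the window follows H24.
- **A yes/no outcome saturated by early use.** Section IV.A.2 defines a dose comparison; only the short wording in III.B suggests yes/no. If yes/no were used and, say, 50% were already treated, new need of 40% versus 20% among the rest would become 70% versus 60%. That argument is secondary.

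**Conclusion.** The point holds as a correctable weakness in one secondary endpoint. The window has no origin, and counting from D0 or H0 puts at least 18 hours before randomisation and at least 24 hours before rewarming into a 72-hour total or mean. The reduction to 0.67d follows from the timeline if the clock starts at H0. The 1.2 to 3.7-fold sample-size range rests on assumed SD ratios of 0.5 to 2 and correlations of 0.3 to 0.85, and on a single 72-hour summary being tested without baseline adjustment. Type I error is unaffected. The primary IL6 comparison and its sample size are not touched. The practical consequence is that a null vasopressor result would be hard to interpret.

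**What to change.** Define the endpoint as weight-indexed noradrenaline or adrenaline dose from the start of rewarming (H24) to H72. Analyse it with the pre-rewarming dose as covariate, and report use before H24 as a baseline characteristic. If a yes/no need is also reported, count it from H24.

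The text change is short, and the analysis plan is to be finalised only when the database is frozen. There are two costs. The result will be less comparable with reports using the first 72 hours. The sponsor must also confirm that the data allow it; it would be wrong to assume that no further collection is needed. The flow chart records treatments under J0, J1, J2 and then discharge from intensive care, counted from the start of cooling. Because D0 precedes H0, H72 falls later than 72 hours after D0, and a daily entry may straddle H24. If only daily records exist, use the recorded days after rewarming starts, adjusted for the earlier day or days, and state that rule in advance.
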